Trial Protocol

Title: "Longitudinal trial assessing cellulite in women wearing a new compression garment - one side with ink printed micro-pads ("Vari-pads") and one side without."

Principal Investigator: [name] MS FRCS(Gen) FCPhleb

Protocol Identifying Number: TWC-SM-2023-01

Protocol version number & date: v 1.1 28 June 2023

Ethics: Not required according to HRA Decision Tools (see Result - England Ethics 21-May-

2023) – and confirmed by e-mail from MHRA.

NCT: To be registered on ClinicalTrials.gov on confirmation of Ethics position

Background:

Cellulite is a very common condition that affects up to 90% of women.¹ It is much less commonly found in men. It presents as a dimpling principally of the skin of the buttocks and thighs, with the appearance having been described as resembling "orange peel", "cottage cheese" or a "quilt". In women who are affected, it usually appears after puberty. It occurs in all races, but is thought to occur more commonly in Caucasians.¹

The product being tested:

The product being tested is to be a retail (non-medical) product presented as standard compression shorts with a pattern of small, raised pads ("Vari-pads") of different heights printed on the inner aspect. A previous trial that we have performed has suggested that wearing these for eight hours a day can reduce the appearance of cellulite.² In addition, subjects found these compression pants to be very comfortable.²

In this trial, we want to see whether the subjective and objective improvement is due to the compression alone, or whether the Vari-pads on the inside of the product enhance the subjective or objective impression of cellulite. As such, we have asked the manufacturer to produce pairs of pants where the Vari-pads are printed onto the inner aspects as per usual on one side only, but not on the other side.

Subjects will then be asked to wear the apparel for at least eight hours a day, at times most suitable for themselves.

If and when they notice a difference between the appearance of cellulite between the two sides, they will notify us and we will then swap them into the 'normal' garments with Vari-pads on both sides, which they are then welcome to continue to wear.

Subjects:

We will be asking for volunteers of who are adult women (over the age of 18 years old), who are able to walk normally and have cellulite of their buttocks and/or upper thighs. We will ask them to check the inclusion and exclusion criteria and, if they believe that they are able to be part of the trial, they will be given an appointment to see the trial coordinator.

Inclusion Criteria:

- Women, over the age of 18 years old, who are able to walk normally and who have cellulite on their buttocks and/or upper thighs.

Due to having to produce special garments for this trial where only half of the garment has the Vari-pads, there will be for following restrictions:

Total number = 60

Volunteers will be asked their sizes (Small, Medium, Large and Extra-large) and will only be invited to attend if there are available places in that size category.

Sizes:

- Small = 15
- Medium = 15
- Large = 15
- Extra-large = 15

Exclusion Criteria:

- Women under 18 years of age.
- Women who are pregnant or who intend to get pregnant in the next 6 months.
- Women with no discernible cellulite on initial examination.
- Women undergoing any other treatment which aims to reduce the appearance of cellulite.
- Women who are unable to complete at least 3 months of this trial.

The Trial:

Volunteers will be asked to email their interest in the trial and will be asked to check that they fit the inclusion and exclusion criteria. If they do, they will be given a free of charge appointment.

Potential volunteers will then be sent the subject information sheet by email so they have ample opportunity to both read about the trials but in addition, to ask any questions before their first appointment. These can be answered by email. In this way, we hope that most volunteers will be suitable to proceed with the trial. We will stop recruitment when a maximum 60 subjects have been enrolled.

The garments will be worn for at least 8 hours per 24 hours. For hygiene reasons, we suggest that briefs/pants are worn under the garment. However, to increase the area of contact between garment and cellulite, we suggest wearing a thong, "high thigh", or similar panties.

There will be 4 visits required:

- 1] First Visit Start of trial
- 2] 3 Months Visit
- 3] 6 Months Visit End of trial
- 4] Variable end-point visit whenever the subject can tell that there is a difference between the left and right sides if the subject does not reach this end point, they will only have 3 visits and will not need the garment with Vari-pads on both sides.

First Visit (day zero):

Subjects will be asked to sign a consent form if they have asked sufficient questions and have decided to go ahead with the trial.

- Their cellulite will be graded as per the Nürnberger F, Müller grading system³

Grading	Description
Scale	
0	No alteration to the skin surface - NO CELLULITE SO THESE
	SUBJECTS will be EXCLUDED
1	Skin is smooth whilst subject is standing/lying, but alterations can be seen
	by pinching the skin, or by muscle contraction
2	'Orange-peel' or mattress appearance is evident upon standing without the
	use of any manipulation (pinching or muscle contraction)
3	Alterations seen in grade two presented together with raised areas and
	nodules

- Standard high-resolution photographs will be taken of their buttocks from behind, side and obliquely in the standing position with the muscles relaxed. The same will then be performed for the thighs. [Subjects will not be photographed in any way so as to be able to identify them.]
 - Subjects will have height and weight measured and noted.
- Localised transcutaneous water content measurement using LymphScanner (Delfin Technologies, Finland) this is a non-invasive device passed over the skin to determine the electrical conductance of the skin and sub-cutaneous tissues.
- They will be given a Celluqol[®] Quality of life questionnaire (long version see appendix)⁴ to complete.
- They will then be given the garment (x2) with one side covered with the Vari-pads, with the other side without any raised pads.

Variable End-point Visit:

When subjects can see or feel a significant difference in the cellulite of their buttocks and/or thighs between the sides, they will contact us and return for assessment.

At this visit, the following will be performed:

- Weight
- Photographs
- Questions as to the routine of garment wearing how many hours per 24 and when
- Transcutaneous water content buttocks and thighs
- Celluqol® QOL Questionnaire
- They will be given 2 new garments with Vari-pads on BOTH sides.

3 Months Visit.

At this visit, the following will be performed:

- Weight
- Photographs
- Questions as to the routine of garment wearing how many hours per 24 and when
- Transcutaneous water content buttocks and thighs
- Cellugol® QOL Questionnaire

6 Months Visit - end of trial and £100 paid if all visits completed. The subject can keep the x2 bilaterally padded garments.

At this visit, the following will be performed:

- Weight
- Photographs
- Questions as to the routine of garment wearing how many hours per 24 and when
- Transcutaneous water content buttocks and thighs
- Celluqol® QOL Questionnaire

Primary endpoint:

- The time taken for patients to notice a self-determined significant difference between their right and left side and request the full garment.

Secondary endpoints:

- Quality of life changes by Celluqol® questionnaire 0, 3 and 6 months.
- Changes in photographs 0, 3, 6 months as assessed by 2 'blinded' observers
- Changes in transcutaneous water measurements

Interim Analysis:

We will perform an initial analysis when all of the results are in from the 1 month and 3 months visit.

Consent form: Please see attached.

Subject information sheet: Please see attached.

Insurance: The Whiteley Clinic has full insurance cover for clinical trials.

Payment: Subjects who complete the trial to 6 months will be allowed to keep the compression garments (worth £90.00 each) and will be given £100 in compensation for their time and travel.

References:

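### The padded side is the only contrast with compression alone, yet no random or balanced left/right assignment is given and the side judged better is not recorded

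*Protocol*

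**What the plan says.** Under 'The product being tested', the Protocol sets out to learn "whether the subjective and objective improvement is due to the compression alone" or whether the pads improve on it. There is no separate control group. The manufacturer has been asked for garments in which "the Vari-pads are printed onto the inner aspects as per usual on one side only, but not on the other side".

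The places that bear on allocation and on direction are these:

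- **First Visit (day zero):** "They will then be given the garment (x2) with one side covered with the Vari-pads, with the other side without any raised pads". Left or right is not mentioned.
- **Inclusion Criteria:** the only garment rule concerns size. Volunteers "will only be invited to attend if there are available places in that size category", with 15 places in each of four sizes.
- **Primary endpoint:** "The time taken for patients to notice a self-determined significant difference between their right and left side and request the full garment".
- **Variable End-point Visit:** the list covers weight, photographs, water content, the quality-of-life questionnaire and "Questions as to the routine of garment wearing how many hours per 24 and when". Every woman who attends this visit receives garments padded on both sides.
- **Secondary endpoints:** "Changes in photographs 0, 3, 6 months as assessed by 2 'blinded' observers", together with changes in water content.

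**The concern.** There are two separate gaps.

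**Allocation.** In a within-person design with one treated and one untreated side, left/right placement does the work of the randomisation list. The Protocol does not say whether the side is constant, mixed, alternated or randomised. If it is constant, any systematic left/right influence looks the same as a pad effect. Examples are a general tendency to judge one body side better, a change over time that favours one side, or a posture or lighting shift from baseline in the same lateral direction across women. An observer who once learned the side would also be unmasked for every photograph set. If sides are mixed without a rule, bias is possible but confounding is not complete.

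**Direction.** The primary endpoint is reached by a difference in either direction. A woman who finds the unpadded side better is counted in the same way as one who finds the padded side better. Even perfect side assignment could not tie this endpoint to the pads unless the direction is known.

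What is at stake is the trial's central question. Allocation is fixed when the garments are made and issued, so a later analysis plan cannot supply it.

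**Working it through.** **The Protocol's own figure.** 4 sizes × 15 = 60, which agrees with the stated total. No power calculation or side-comparison test is given, so there is nothing further to reproduce. What follows is an illustration under stated assumptions.

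**Inputs.** n = 60 is from the Protocol. The rest are assumptions:
- no true pad effect;
- each woman who reports a difference names a better side;
- a probability q of 0.55, 0.60 or 0.65 that one given body side is preferred for reasons unrelated to the pads;
- 60 or 30 women reporting;
- an exact two-sided sign test at 5%.

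**Step 1: rejection limits.** Find the smallest r with 2·P(Bin(n, 0.5) ≥ r) ≤ 0.05.
- n = 60: r = 39 gives 0.0273 (r = 38 gives 0.0519).
- n = 30: r = 21 gives 0.0428 (r = 20 gives 0.0987).

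**Step 2: false rejection.** Let X be the number of women who judge the padded side better. The false rejection rate is P(X ≥ r) + P(X ≤ n − r).
- Constant side: X ~ Bin(n, q).
- Split a:b between the two sides: X = Bin(a, q) + Bin(b, 1 − q), by exact convolution.
- 30 reporters drawn at random from a 30:30 allocation: the same sum, weighted by the hypergeometric distribution of a.

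| Allocation of padded side | Reporting | q = 0.55 | q = 0.60 | q = 0.65 |
|---|---|---|---|---|
| Constant | 60 | 7.7% | 25.7% | 55.9% |
| Unplanned 45:15 mix | 60 | 3.8% | 7.4% | 13.9% |
| Random 30:30 | 60 | 2.7% | 2.4% | 2.1% |
| Constant | 30 | 7.4% | 17.7% | 35.8% |
| From random 30:30 | 30 | 4.2% | 4.1% | 3.8% |

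**Step 3: change from baseline (photographs, water content).** Subtracting baseline removes an asymmetry that stays constant. Suppose instead that one body side changes relative to the other by d standard deviations of the within-woman side difference, again with no pad effect. For a paired t test with n = 60 and a constant side, the noncentrality is d·√60, that is 0.775, 1.549 and 2.324 for d = 0.1, 0.2 and 0.3. The critical value is 2.001 on 59 degrees of freedom. The 30:30 row is from 200,000 simulated trials.

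| Allocation | d = 0.1 | d = 0.2 | d = 0.3 |
|---|---|---|---|
| Constant | 11.9% | 33.2% | 62.8% |
| 30:30 | 4.8% | 4.5% | 4.1% |

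**Step 4: direction, from the text.** The endpoint needs a noticed difference and a request for the full garment. The request might seem to imply that the pads are preferred. However, both 'The product being tested' and 'Variable End-point Visit' move every woman who reports a difference into garments padded on both sides. The request therefore does not distinguish the two directions, and no listed item does so explicitly. Steps 1 and 2 could not be carried out on the primary endpoint as it is now recorded.

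**The case against.** The strongest reply is that the Protocol never says the side is constant. What is established is silence, and complete confounding follows only if the side is in fact constant. That stands, and it limits the claim.

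Baseline measurements remove constant asymmetry, and asymmetry that differs in direction between women does not bias the average. Posture or lighting matters only if it shifts in one lateral direction across most women, and nothing in the Protocol suggests that it does. This also stands. The risk is a systematic lateral change or preference, not asymmetry as such.

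The percentages rest on preferences, shifts and a 45:15 mix that have no source in the Protocol, and the sign test is not the planned endpoint. They show how sensitive the design is and are not this trial's error rate.

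A woman who thought the pads made her worse has less reason to ask for pads on both sides, and photographs and water content are taken at the end-point visit. These hint at direction. They do not record her own judgement, and the photograph endpoint names only months 0, 3 and 6 and defines no padded-versus-unpadded reading.

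Finally, women can feel which side is padded, and reporting a difference brings new garments. Randomisation leaves that untouched, so it mainly protects the photograph and water endpoints. The primary endpoint also needs the recorded direction, and even then the wearer is not blinded.

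**Conclusion.** The concern holds, on both counts. The Protocol gives no random or balanced assignment of the padded side, although this is its only treatment allocation. Its primary endpoint and visit list also leave unrecorded which side the woman judges better. As written, a report against the pads can count the same as one in their favour, and the pad effect may be confounded with body side.

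The second count rests on the text alone. The size of the first depends on how the garments are actually made and on how strong any lateral preference or change is. Under the assumptions above, with all 60 reporting, a constant side raises false rejection to between 7.7% and 55.9%, while a 30:30 split keeps it at or below 2.7%. This should be corrected before garments are issued. It is not shown that the trial will use one constant side.

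**What to change.** - Produce a left-padded and a right-padded version in each size. Randomise the side within size, 8:7 in two sizes and 7:8 in the other two (8 + 8 + 7 + 7 = 30 per side). Give both of a woman's garments the same padded side.
- Reveal the side only after the baseline assessments. Garment issue is already listed last at the first visit, so this only needs to be stated as a rule.
- Withhold the side code from the two photograph observers.
- At the variable end-point visit, record which side the woman judges better, and report the two directions separately.
- Record photographs and water content by side. Analyse the padded-minus-unpadded change from baseline using visits up to her switch to bilateral pads, because the side contrast ends there.
- State as a limitation that the wearer knows which side is padded.

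The cost is a mirrored print layout, two stock versions per size, a short randomisation list and one added question. The number of participants is unchanged. The manufacturer has already been asked for the garments, so the order may have to be revised.

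### Entry requires availability for only 3 months although the final visit and the dated secondary endpoints are at 6 months, so a capped place can go to a woman already known to be unavailable at the end

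*Protocol*

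**What the plan says.** The Exclusion Criteria contain one rule on availability, which excludes "Women who are unable to complete at least 3 months of this trial". The same list has a rule with a longer horizon: "Women who are pregnant or who intend to get pregnant in the next 6 months".

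The section headed The Trial states "There will be 4 visits required" and lists among them "6 Months Visit End of trial". The fourth is the variable end-point visit; "if the subject does not reach this end point, they will only have 3 visits", which leaves day 0, month 3 and month 6.

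The primary endpoint is "The time taken for patients to notice a self-determined significant difference between their right and left side and request the full garment". It carries no time limit of its own, so observation is bounded by the 6-month end of trial. Two secondary endpoints are dated: "Quality of life changes by Celluqol® questionnaire 0, 3 and 6 months" and "Changes in photographs 0, 3, 6 months as assessed by 2 'blinded' observers". The third, transcutaneous water content, has no dates in its endpoint wording, although it is measured at every visit.

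Under Inclusion Criteria, places are limited to 15 in each of four sizes because special garments have to be made. Recruitment stops at 60, and no replacement of women who leave is described. The £100 and keeping the garments are tied to completing 6 months.

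**The concern.** The availability threshold is half the length of the trial, and the protocol gives no reason for it. Month 3 is not named as the main time point. As written, a woman who can attend for 3 months but not for 6 is eligible.

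She would occupy a place that cannot be refilled, in a trial whose size is set by garment supply. Her month-6 quality-of-life and photograph values would be absent from the outset. On the primary endpoint, any event she would have had between months 3 and 6 would go unseen. An analysis plan can say how to handle these missing values, but it cannot recover them. Eligibility is fixed in the protocol, so the remedy belongs there.

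**Working it through.** **Reproducing the protocol's figure.** No power-based sample size is given. The total is the sum of the size quotas: 4 × 15 = 60, which agrees with the stated 60.

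**Inputs from the protocol.** N = 60 women (Inclusion Criteria); minimum availability 3 months (Exclusion Criteria); end of trial 6 months (The Trial).

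**Assumed input.** Let s be the number of women available for 3 months only. The protocol gives no value, so 10%, 20% and 30% of 60 are used to show a range: s = 6, 12 or 18.

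**Formulas.**
- Women who can give 6-month data: n6 = 60 − s.
- Maximum woman-months at risk: 6 × (60 − s) + 3 × s, against 6 × 60 = 360 when s = 0.
- Width of a 6-month confidence interval relative to the full 60: √(60 / n6), taking width as proportional to 1/√n with unchanged variability.

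**Results, before any ordinary dropout.**

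| Assumed share | s | n6 | Maximum woman-months | Lost from 360 | Relative interval width |
|---|---|---|---|---|---|
| 0% | 0 | 60 | 360 | 0 | 1.00 |
| 10% | 6 | 54 | 6×54 + 3×6 = 342 | 18 (5%) | √(60/54) = 1.05 |
| 20% | 12 | 48 | 6×48 + 3×12 = 324 | 36 (10%) | √(60/48) = 1.12 |
| 30% | 18 | 42 | 6×42 + 3×18 = 306 | 54 (15%) | √(60/42) = 1.20 |

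**Reading the woman-months column.** These losses are upper bounds. The total of 360 supposes that nobody has the primary event within 6 months. A woman who notices a difference before month 3 is fully observed for the primary endpoint and loses nothing on it by leaving at month 3. Only a woman without an event by then is censored early. The fall in n6 has no such allowance: for quality of life and photographs at 6 months, each such woman's value is simply missing.

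**With the rule aligned to 6 months.** No woman is knowingly unavailable at the end, so the planned 6-month number is 60 and the maximum is 360 woman-months, again before ordinary dropout.

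**The case against.** The criterion sets a floor. It does not show that anyone will enrol for 3 months only. The protocol lists the 6-month visit as required and withholds the £100 and the garments until 6 months are completed, and both work against early leaving. The information sheet and consent form, which might ask for a 6-month commitment, are not shown. Month 3 is also a scheduled visit, a dated time point for both dated secondary endpoints and part of the planned interim analysis, so a 3-month minimum could be a deliberate trade-off when filling fixed size quotas. The pregnancy rule has its own purpose and need not share a horizon with availability. All of this stands, and it limits how firmly the size of the loss can be stated. It does not supply a reason for the threshold in the protocol, and it does not stop a capped place from going to a woman who has said she cannot attend the last visit.

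Two stronger readings are tempting, and the protocol supports neither:

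- A reader might infer bias, with women who see no benefit stopping at 3 months. The criterion concerns ability known at entry, before the garment is worn, and that cannot be caused by seeing no benefit. Nothing makes month 3 a sanctioned exit, and a 6-month entry rule would not keep disappointed women in the trial.
- A reader might want to express the loss as power for a 6-month comparison of the two sides. The protocol has no 6-month side-preference endpoint, and women who reach the primary endpoint change to garments padded on both sides. A month-6 left-right comparison of all 60 would therefore not be a contrast of pads with no pads.

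**Conclusion.** The mismatch is in the text and is worth correcting. What it puts at risk is an avoidable loss of 6-month data and precision. If 10% to 30% of the women were available for 3 months only, 6 to 18 of the 60 would have no 6-month quality-of-life or photograph data, and the corresponding intervals would be about 5% to 20% wider. The loss for the primary endpoint would be at most 5% to 15% of woman-months, and less to the extent that events come early. These figures rest on an assumed share with no anchor in the protocol; if no such woman enrols, nothing is lost. The two dated secondary endpoints bear most of the effect.

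**What to change.** Reword the availability criterion so that it excludes women who do not expect to be able to complete the 6 months of the trial, and use the same wording in the screening text. State that women who enter in good faith and later leave early stay in the analysis, with all their follow-up to the date of leaving. If 3 months was chosen deliberately, the alternative is to say why it suffices and to name month 3 as the main time point for the secondary endpoints.

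The change is a small edit to one criterion. Its downside is that a few volunteers will be turned away and recruitment within the size quotas may be slightly slower.

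### The primary event is any self-perceived left-right difference, not a change since day 0, so the endpoint as defined does not separate asymmetry present at entry from a pad effect

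*Protocol*

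**What the plan says.** The Primary endpoint section defines the outcome as "The time taken for patients to notice a self-determined significant difference between their right and left side and request the full garment". The Variable End-point Visit section gives the trigger: "When subjects can see or feel a significant difference in the cellulite of their buttocks and/or thighs between the sides, they will contact us". The list of visits under The Trial describes the same visit as taking place "whenever the subject can tell that there is a difference between the left and right sides". The section on the product says much the same in looser terms.

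Inclusion is open to women "who are able to walk normally and who have cellulite on their buttocks and/or upper thighs". Neither the inclusion nor the exclusion list mentions similarity of the two sides.

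At the First Visit the protocol states "Their cellulite will be graded as per the" published 0–3 scale. Its one stated use is to exclude grade 0, and the scale entries describe the woman rather than a side, for example "Skin is smooth whilst subject is standing/lying, but alterations can be seen" in grade 1. The same visit includes photographs of buttocks and thighs from several angles, including from behind, and a localised skin water measurement. Photographs and water content are repeated at the event, 3-month and 6-month visits. Under Secondary endpoints, two blinded observers assess photograph changes at 0, 3 and 6 months; the event visit is not in that list.

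**The concern.** The scientific question is whether the pads add anything to compression, and it is answered by comparing the two sides of each woman. A within-woman comparison of this kind is informative about the pads only if the starting difference between sides is known and allowed for. Here the event depends on the difference at the moment of reporting, not on how far it has moved since day 0.

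A woman whose sides already differed may look more closely once she is in a left-right trial and report that difference. Her report would count as a primary event and would shorten the apparent time to notice, even if the pads did nothing. No separate group shows how often this happens without pads.

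There is a second effect. The event leads to garments padded on both sides, so an event caused by entry asymmetry also ends that woman's padded-versus-unpadded comparison for the photographs and water measurements.

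**Working it through.** **Step 1: the event definition, wording by wording.** Three features would separate a pad effect from entry asymmetry.

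| Place in protocol | Difference must be new? | Compared with day 0? | Direction recorded? |
|---|---|---|---|
| The product being tested | not stated | no | no |
| The Trial, list of visits | not stated | no | no |
| Variable End-point Visit | not stated | no | no |
| Primary endpoint | not stated | no | no |

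**Step 2: whether anything at entry prevents the problem.** There is no symmetry criterion. The First Visit list contains no question on whether the woman already sees or feels a difference. The grade is not stated to be recorded by side. The protocol gives no rule for which side carries the pads, so it offers no stated balancing that would make entry asymmetry favour each side equally often.

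**Step 3: what baseline information exists.** The day-0 photographs from behind should show both sides. The water measurement may be side-specific, but the First Visit section does not name sides. Both could serve as a baseline, but the protocol links neither to the primary event.

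**Step 4: possible size.** The only figure in the protocol that bears on this is the number of women: four sizes × 15 = 60, which agrees with the stated total. No asymmetry rate is given, so let q be an assumed share of women with a noticeable difference at entry.

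- Expected number able to report an event on that basis alone = 60 × q.
- Chance that there are at least five such women = P(X ≥ 5), with X binomial(60, q).

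| Assumed q | 60 × q | P(X ≥ 5) |
|---|---|---|
| 5% | 3 | 0.18 |
| 10% | 6 | 0.73 |
| 20% | 12 | 0.996 |

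These are counts of women who could report such an event, not a forecast of how many would.

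**The case against.** The strongest reply is that the product section speaks of women noticing a difference while wearing the garment, which naturally suggests one that has developed. The primary endpoint also needs more than a slight asymmetry: she must judge it significant and request the full garment, which means contacting the clinic and returning. The subject information sheet, which is not in the text at hand, may tell women to look for a change. All of this stands as a reason why not every asymmetric woman would become an event. It does not alter the definition, which turns on whether women "notice a self-determined significant difference between their right and left side" and leaves the day-0 state out.

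Some stronger readings are not supported:

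- A reader might infer that cellulite is graded once per woman and never by side. The protocol does not say so; it is silent.
- A reader might infer that entry asymmetry can never be separated from a pad effect. The day-0 photographs, and perhaps the water measurements, would allow at least a partial reconstruction.
- A reader might blame the single grading. A 0–3 grade for each side would still miss differences within a grade, and the woman's own perception would still decide the event. The fault lies in the endpoint definition.
- A reader might call it an error that the grade is not repeated later. The grade is not an endpoint, so repeating it is a matter of preference.

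**Conclusion.** The point holds in this form: the primary event is not anchored to the day-0 state of the two sides, so the endpoint as defined does not separate a difference present at entry from one produced by the pads. Followed as written, the plan can give a misleading time to notice. A later analysis plan could draw on the photographs, but it could not recover a day-0 perception that nobody asked about.

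The size is unknown. The range of 3 to 12 women out of 60 rests entirely on an assumed 5% to 20% with a noticeable difference at entry and on full recruitment. It illustrates the exposure and does not measure the bias. The change is worth making because it is cheap and bears on the primary result.

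**What to change.** - **Day 0, before the garment is issued:** ask each woman whether she already sees or feels a difference between left and right, and in which direction. Record the existing grade for each side.
- **Photographs:** have the two blinded observers already planned rate left versus right on the day-0 and event-visit photographs.
- **Primary event for analysis:** define it as a self-perceived difference that is new or changed from the woman's day-0 record, with its direction noted. Her own report remains the basis of the endpoint; the observers' ratings support it.
- **Side comparisons:** use the day-0 side difference when comparing sides on photographs and water content.
- **Garment-swap procedure:** leave it as it is. Some women may then swap on an unchanged difference without a counted event, so the analysis should state how their time is handled and report their number.

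The cost is a few minutes at visits already held, some extra reading by the same observers, and possibly fewer counted events.

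### The primary event is one self-report that is neither rechecked nor given a direction, so passing or wrong-side perceptions count the same as a pad effect

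*Protocol*

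**What the plan says.** The Protocol's Primary endpoint section defines the event as "The time taken for patients to notice a self-determined significant difference between their right and left side and request the full garment". Under Variable End-point Visit the trigger reads "When subjects can see or feel a significant difference in the cellulite of their buttocks and/or thighs between the sides, they will contact us"; the sentence ends "between the sides, they will contact us and return for assessment".

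Two other places state the trigger without the word *significant*. The product section has "If and when they notice a difference between the appearance of cellulite between the two sides, they will notify us", and the visit list in The Trial has "Variable end-point visit whenever the subject can tell that there is a difference between the left and right sides".

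The end-point visit lists weight, photographs, wearing routine, water content and the Celluqol questionnaire. It then says "They will be given 2 new garments with Vari-pads on BOTH sides". No finding at the visit is named as a condition for counting the event or for the swap.

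The window closes at "6 Months Visit End of trial", and enrolment is "Total number = 60". Blinded reading of photographs is named only under Secondary endpoints, for 0, 3 and 6 months.

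**The concern.** The stated aim is to separate the effect of the pads from that of compression alone. Every woman wears one padded and one unpadded side, so no group without pads shows how often women report a difference when pads do nothing. The event itself therefore has to distinguish a pad effect from ordinary fluctuation, and as defined it cannot do so in two respects.

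- **Persistence.** A difference that has gone by the time she attends counts the same as one that has lasted.
- **Direction.** The endpoint asks for a difference between right and left, not for the padded side to be better. Nothing listed at the visit records which side she preferred.

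False events can only bring the observed time forward, because the time recorded is the earlier of a false report and a true one. Each also puts that woman into bilateral pads. After that, her later photographs and water readings no longer compare a padded with an unpadded side.

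**Working it through.** The Protocol gives no event rate, error rate, effect size or sample-size calculation, so there is no figure to reproduce. What follows illustrates the mechanism.

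**From the document:** 60 women; 6 months, taken as 26 weeks or 182 days.

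**Assumed:** no pad effect; a weekly chance q of a null report that meets the *whole* event definition (judged significant, contact made, garment requested); independent weeks; a share c of such reports still present at the visit.

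**Step 1. Events as now defined:** P = 1 − (1 − q)^26.

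| q per week | P | of 60 women |
|---|---|---|
| 1% | 1 − 0.99^26 = 23.0% | 13.8 |
| 3% | 1 − 0.97^26 = 54.7% | 32.8 |
| 5% | 1 − 0.95^26 = 73.6% | 44.2 |

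Smaller rates give much less: q = 0.1% gives 2.6% (1.5 of 60). If women in effect judge only monthly (6 looks), chances of 1% and 5% per look give 5.9% and 26.5%.

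**Step 2. Events confirmed at the visit.** As written, every woman who attends is given bilateral garments, so an unconfirmed woman leaves the comparison. The confirmed share is then c × P.

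| q | c = 0.5 | c = 0.25 |
|---|---|---|
| 1% | 11.5% | 5.8% |
| 3% | 27% | 14% |
| 5% | 37% | 18% |

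If unconfirmed women instead stayed at risk, the share would be 1 − (1 − qc)^26: 12%, 32% and 48% for c = 0.5, and 6%, 18% and 28% for c = 0.25. Those figures do not apply under the present garment wording.

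**Step 3. Dependence between days.** Perceptions on neighbouring days are unlikely to be independent. A latent side difference with no pad effect was simulated as a first-order autoregressive process (20,000 women, 182 days), with an event when its absolute value first passed a threshold.

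| Daily chance | autocorrelation 0 | autocorrelation 0.95 |
|---|---|---|
| about 1.2% | 89.6% (53.7 of 60) | 40.4% (24.2 of 60) |
| about 0.27% | 39.4% (23.6 of 60) | 13.0% (7.8 of 60) |

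Autocorrelation reduces the accumulation substantially but does not remove it.

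**The case against.** **The event is more than a fleeting impression.** She must judge the difference significant, contact the clinic and request the garment. This stands, and it is why q above is the chance of the full report. The filter is weak, however: *significant* is self-determined with no scale, two passages omit the word, and reporting brings two further garments, which the Payment section values at £90 each. The Protocol does not say when the request is made. If it is made at the visit it is some reaffirmation, but still gives no side.

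**A reader might infer continuous self-checking with unlimited looks.** The documents do not support that. They allow a report at any time but set no checking frequency, so the number of looks is unknown.

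**The visit does include an assessment.** Photographs and water content are listed before the garments. But neither is a condition for the event, and blinded reading is not named for this visit.

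**Noticing is the target, so confirmation changes it.** This is partly right. No stated error rate is inflated, because none is stated, and this is a design weakness rather than an error of arithmetic. But the trial's own question concerns the pads, and noticing without persistence or direction answers it poorly.

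**Asking the same unblinded woman again is a weak filter.** This also stands. Expectation from feeling the pads, or a left-right asymmetry present at entry, would persist and be confirmed.

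**Conclusion.** The point holds in a limited form. By the Protocol's own wording, one self-judged report plus a request is the primary event, its persistence and direction go unrecorded at the visit, and the swap follows without condition. Passing or wrong-direction perceptions therefore enter the primary result as events.

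How many do so is unknown. The 23%, 55% and 74% rest on assumed, independent weekly chances. The confirmed 12%, 27% and 37% rest further on half of the reports persisting and on every woman being swapped. None of these figures is evidence about this trial, and it would be wrong to read them as showing that most reported events will be false.

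The sponsor should make the change. The trial can run without it, but its primary result would be harder to interpret.

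**What to change.** 1. At first contact, record the date and which side she judges better, left or right.
2. Make a neutral question the first item of the end-point visit, before photographs and before any garment is issued: today, is the left side better, the right side better, or neither; and is the difference significant?
3. Count the primary event only if a significant difference is reported again on the same side, dated to first contact.
4. Report how many events favour the padded side.
5. Show all reported events, confirmed or not, as a sensitivity analysis.

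The sponsor must also reconcile the passages that ask for any difference with those that ask for a significant one, and the garment-issue wording with the event definition. What is done about garments for a woman whose report is not confirmed is for the sponsor to settle.

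**Cost:** one question at contact, one at a visit already planned, revised endpoint wording, and fewer counted events. The change filters passing perceptions and shows direction. It does not remove expectation bias or pre-existing asymmetry, and confirmed events should not be described as free of either.
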